9.4.2. Safety Analyses

The safety analysis will be performed using the safety population and will be fully defined in the SAP. The safety parameters will include AEs and vital signs. For vital signs data, the last nonmissing safety assessment before the first dose of study intervention will be used as the baseline.

9.4.2.1. Adverse Events

An AE will be considered a TEAE if:

- The AE began on or after the date of the first dose of study intervention; or
- The AE was present before the date of the first dose of study intervention, but increased
 in severity or became serious on or after the date of the first dose of study intervention

An AE will be considered a TESAE if it is a TEAE that additionally meets any SAE criteria.

The number and percentage of participants reporting TEAEs in each study intervention group will be tabulated by system organ class and preferred term and by system organ class, preferred term, and severity.

The number and percentage of participants reporting treatment-related TEAEs in each study intervention group will be tabulated by system organ class and preferred term.

BOTOX

If more than 1 AE is coded to the same preferred term for the same participant, the participant will be counted only once for that preferred term using the most severe and most related occurrence for the summarizations by severity and by relationship to study intervention.

Summary tables will be provided for participants with SAEs and participants with AEs leading to discontinuation if 5 or more participants reported such events. Listings of all AEs, SAEs, and AEs leading to discontinuation by participant will be presented.

The definitions of an AE and SAE can be found in Appendix 2.

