labia inferior paresis, and subject noticed possible loss of movement along jawline]). In addition, there was no safety risk identified in participants who received 2 BOTOX treatments for MMP within 1 year.

Similar safety results have been described in the medical literature following BOTOX treatment of MMP in 1178 participants with various doses (ranging from 10 to 100 U/masseter) and numbers of treatment cycles (Section 5.2.2 of the BOTOX MMP investigator brochure). The most frequently reported AEs were pain, discomfort, or muscle ache at the sites of injection. Because the masseter muscle is 1 of the primary muscles of mastication, its treatment resulted in some reports of transient masticatory difficulties (ie, weakness chewing), which was the next most frequently reported AE in these publications. BOTOX injection of the masseter and/or adjacent facial muscles also resulted in some cosmetic complaints, which were reported less frequently. In general, adverse reactions occur within the first few days to weeks following injection of BOTOX and, while generally transient, may have a duration of several months or, in rare cases, longer. More detailed information about the known and expected benefits and risks and reasonably expected AEs with BOTOX treatment may be found in the investigator's brochure and package insert.

3. Objectives and Endpoints

Objectives	Endpoints
Primary	
To compare the efficacy of BOTOX with placebo in participants with bilateral MMP	 Proportion of responders who achieve ≥ 2-grade improvement from baseline at Day 90, per investigator assessments of MMP using the MMPS (5 severity grades: 1 = minimal, 2 = mild, 3 = moderate, 4 = marked, 5 = very marked)
 To compare the safety of BOTOX with placebo in participants with MMP 	Incidence of AEs and change from baseline in vital signs
Secondary	
 To compare the efficacy of BOTOX with placebo in participants with MMP 	 Proportion of responders who achieve MMPS Grade ≤ 3 at Day 90 according to investigator Proportion of responders who achieve MMPS-P Grade ≤ 3 at
	Day 90, according to participant
	 Proportion of responders who achieve ≥ 2-grade improvement from baseline at Day 90 using the MMPS-P
	 Proportion of responders who achieve PSAC Grade ≥ 1 (at least minimally improved from baseline) at Day 90
	 Change from baseline in lower facial width (mm) at Day 90, calculated from standardized images
	Duration of effect for BOTOX-treated MMPS responders
Other (COA)	

4. Study Design

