4.1. Overall Design

This is an 18-month, multicenter study consisting of 2 periods (see schema, Section 1.2). Period 1 (Days 1 through 180) is a double-blind, randomized, placebo-controlled, single-treatment design, which will assess the safety and efficacy of BOTOX treatment of MMP. Period 2 (Days 180 through 540) is open-label with up to 2 BOTOX retreatments if the participant meets retreatment criteria (Section 6.6). Over the duration of the study, a maximum of 3 study treatments will be administered to each study participant.

Approximately 360 participants will be enrolled at approximately 30 sites in order to have 306 participants complete the study based on an anticipated dropout rate of 15%. Of the enrolled participants, approximately 235 will be enrolled from China (mainland), approximately 75 will be enrolled from Canada, and approximately 50 will be enrolled from Taiwan region.

On Day 1, participants will be randomized in a 3:1 ratio to receive BOTOX 72 U or placebo. Randomization will be stratified at each investigator site by the participant's baseline MMPS Grade (4 or 5). Following completion of Period 1, all participants will continue in Period 2, which will assess the efficacy and safety of repeat administration of BOTOX for the treatment of MMP.

Up to 20 scheduled visits are planned: screening (Day -14 to Day -1), baseline (Day 1), follow-up monthly thereafter (Days 30, 60, 90, 120, 150, 180, 210, 240, 270, 300, 330, 360, 390, 420, 450, 480, 510), and study exit (Day 540).

After verification that the participants meet all inclusion and exclusion criteria and completion of all baseline study procedures, participants will be randomized and enrolled. Once enrolled, participants will spend approximately 18 months in the study.

Period 1 (Days 1 through 180)

Treatment will be administered intramuscularly to the bilateral masseter muscles as 6 total injections (0.3 mL per injection), with 3 injections administered per masseter in the area of maximal muscle bulge (Figure 6-1, Section 6.1), for a total injection volume of 1.8 mL. Each 0.3 mL injection will contain BOTOX 12 U or placebo. In Period 1, treatment will be administered on Day 1, and participants will return for follow-up assessments (see Table 1–1) on Days 30, 60, 90, 120, 150, and 180. On Day 180, final Period 1 assessments will be collected, after which all participants will continue into Period 2, the open-label treatment portion of the study.

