9.2. Sample Size Determination

approximately 360 participants (270 BOTOX and 90 placebo) will provide > 90% power

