9.4.2.2. Vital Signs

Descriptive statistics for vital signs (systolic and diastolic blood pressure, pulse rate, and respiratory rate) at baseline and changes from baseline at each assessment will be presented by study intervention.

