#### 10.2 ADVERSE EVENTS

Adverse events will be coded by system organ class and preferred term using the *Medical Dictionary for Regulatory Activities*, version 25.1 or newer.

An AE will be considered as a treatment-emergent adverse event (TEAE) if the AE began or worsened (increased in severity or became serious) on or after the date of the first dose of double-blind study treatment.

A TEAE for treatment cycle 1 is an adverse event with onset after the initiation of study treatment or became serious after the initiation of study treatment for cycle 1.

In each of the analysis periods (treatment cycle 1 in the double-blind period, open-label period, BOTOX cycle, or BOTOX overall), a specific TEAE will only count once per participant, associated with its worst severity during the time period of interest. Unless stated otherwise, the methods of analyses described in this section will be applied to each of the study period.

TEAEs will be summarized for each treatment group by treatment cycle 1 in the double-blind period, open-label period, by BOTOX cycle, and BOTOX exposure overall. Participants will be counted according to the treatment received at baseline (Placebo or BOTOX 72 U) for treatment cycle 1. For open-label period and Any BOTOX exposure tables, participants will be summarized according to the treatment received at cycle 1 baseline and treatment received during open-label (Placebo/BOTOX 72 U or BOTOX 72 U/BOTOX 72 U and Total). The only

exception is BOTOX cycle 3, where participants will be summarized by BOTOX 72 U/BOTOX 72 U.

Overall summary of AEs will be provided on a per-participant basis for categories of TEAEs, treatment-related TEAEs, deaths, serious adverse events (SAEs), AEs leading to discontinuation, and possible distant spread of toxin (PDSOT).

The number and percentage of participants reporting TEAEs in each treatment group will be tabulated by system organ class (SOC) and preferred term, and further categorized by severity and causal relationship to the study treatment separately. If more than 1 AE is coded to the same preferred term for the same participant, the participant will be counted only once for that preferred term using the greatest severity and strictest causality for the summarization by severity and causal relationship.

The incidence of TEAEs will be summarized by preferred term and treatment.

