## 10.5 VITAL SIGNS

Descriptive statistics for vital signs (systolic and diastolic blood pressures, respiratory rate, pulse rate, and weight) values at baseline, postbaseline, and changes from baseline values at each postbaseline timepoint will be presented by treatment group.

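### Comparing safety with placebo is a primary objective, but no readable safety section plans a between-arm estimate or its uncertainty, and cycle 1 follow-up can differ between arms

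*Protocol*

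**What the plan says.** Protocol sections 1.1 and 3 and SAP 5.1 put this objective under the Primary heading: "To compare the safety of BOTOX with placebo in participants with MMP". Its endpoints are "Incidence of AEs and change from baseline in vital signs".

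The planned outputs are all by arm:

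- **Adverse events.** Protocol 9.4.2.1: "The number and percentage of participants reporting TEAEs in each study intervention group will be tabulated by system organ class and preferred term". SAP 10.2: "The number and percentage of participants reporting TEAEs in each treatment group will be tabulated by system organ class (SOC) and preferred term". SAP 10.2 also breaks the tables down by cycle, period, severity and causality, and covers serious events and discontinuations. SAP 10.3 and 10.4 tabulate possible distant spread of toxin (PDSOT) and adverse events of special interest (AESIs) by treatment group.
- **Vital signs.** Protocol 9.4.2.2 gives descriptive statistics "at baseline and changes from baseline at each assessment will be presented by study intervention". SAP 10.5 does the same: "changes from baseline values at each postbaseline timepoint will be presented by treatment group".

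Protocol 9.4.2 leaves the full definition of the safety analysis to the SAP. Pairwise comparison and testing appear in the efficacy sections only (Protocol 9.4.1, SAP 9.0). SAP 17.3 fixes the direction of treatment differences as BOTOX minus placebo, but attaches no difference or interval to any safety output.

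On follow-up, SAP 10.0 ascribes safety data collected after Day 180 and before retreatment to the double-blind treatment. SAP 17.2 ends a cycle on the day before the next treatment, or at study exit if there is none.

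**The concern.** An objective worded as a comparison should name the quantity compared and say how precisely it will be known. Here the reader is left to judge two percentage columns by eye, one of them based on a third as many people. For uncommon preferred terms the smaller column will often show zero by chance alone, so a list of events seen only on BOTOX can arise with no true excess. The zero itself may also be read as firmer evidence than 90 people can give.

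The second issue concerns what the cycle 1 columns cover. Retreatment requires an investigator grade of at least 4 on both sides (Protocol 6.6.1). If BOTOX works, BOTOX participants will tend to qualify later and remain in cycle 1 longer. They then have more time to accrue events in the columns set against placebo.

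Period 1 is the only randomised safety comparison in the study, and it feeds the benefit/risk statement for an elective aesthetic use.

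**Working it through.** **Inputs.** Allocation, Protocol 4.1: "participants will be randomized in a 3:1 ratio to receive BOTOX 72 U or placebo". Arm sizes, Protocol 9.2: "approximately 360 participants (270 BOTOX and 90 placebo) will provide > 90% power". Completers and dropout: 306 and 15% (Protocol 1.1 and 4.1). Illustrative rate: treatment-related mastication disorder in Phase 2, 8/150 = 5.3%, all doses pooled (Protocol 2.3). The documents give no placebo adverse-event rate, so the other rates below are assumptions shown as a range.

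**The plan's own figure.** 306 / (1 − 0.15) = 360. Split 3:1, this gives 270 and 90, as stated. The power statement cannot be reproduced because the assumed response rates are not visible; nothing below depends on it.

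**Chance of a BOTOX-only event when the true rate p is the same in both arms.**

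BOTOX only: (1 − p)^90 × [1 − (1 − p)^270]. Placebo only: (1 − p)^270 × [1 − (1 − p)^90].

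At p = 1%: 0.99^90 = 0.405 and 0.99^270 = 0.066. BOTOX only is 0.405 × 0.934 = 0.378; placebo only is 0.066 × 0.595 = 0.039.

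| True rate, both arms | BOTOX only | Placebo only |
|---|---|---|
| 0.5% | 47% | 9% |
| 1% | 38% | 4% |
| 1.5% | 25% | 1% |
| 2% | 16% | 0.4% |
| 5.3% | 0.7% | below 0.1% |

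**What 0/90 can rule out.** The upper limit of the two-sided 95% Clopper-Pearson interval is 1 − 0.025^(1/90) = 4.0%.

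**What an interval would show** (BOTOX minus placebo, Miettinen-Nurminen 95% CI, percentage points). The 14 is the count expected at the Phase 2 rate: 270 × 8/150 = 14.4.

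| BOTOX | Placebo | Difference | 95% CI |
|---|---|---|---|
| 3/270 | 0/90 | 1.1 | −3.0 to 3.2 |
| 14/270 | 0/90 | 5.2 | 1.0 to 8.5 |
| 14/270 | 1/90 | 4.1 | −1.1 to 7.7 |

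A single placebo case moves the lower limit from above zero to below it.

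**Effect of a frequency cut-off.** If intervals were given only for terms in at least 2% of either arm, a BOTOX-only term would need 6 or more cases (2% of 270 is 5.4). At a true 1% in both arms, the chance of a BOTOX-only term with 6 or more cases is 2.3%, against 37.8% for any BOTOX-only term. So 1 − 2.3/37.8 = 94% of such terms would still have no interval, including the 3/270 versus 0/90 example.

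**Follow-up.** Under SAP 17.2, a participant retreated at Day 180 leaves cycle 1 then. One never retreated stays in it until study exit at Day 540, a possible difference of 360 days. The documents give no figure from which to predict the average imbalance between arms.

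**The case against.** Several points on the other side stand.

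- **No bias from 3:1.** A reader might infer that unequal arm sizes distort the rates. They do not: percentages use each arm's own denominator. Only precision differs.
- **The artefact is limited.** It matters for rates up to about 2 to 3% and is negligible near 5%, so the mastication figure illustrates interval width and not spurious BOTOX-only events.
- **The intervals can be derived.** Anyone with n and N can compute them. That is true, but a primary objective should not depend on readers doing so.
- **The plan may not be fully visible.** SAP 4.0 places table specifications in a separate document, and parts of the SAP are unreadable. It cannot be said that no comparative output exists, only that no readable passage specifies one.
- **Safety is not framed as a formal hypothesis.** Protocol 4.1.1 and SAP 5.2 ask for an acceptable safety profile, and side-by-side randomised columns are a comparison of a kind. This argues against tests, not against an estimate. The stated objective is still comparative.

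The sign convention in SAP 17.3 is the nearest thing to a rebuttal. It settles the direction of a difference without saying that any safety difference will be reported.

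**Conclusion.** The point holds as a cheap improvement. A primary objective to compare safety has no readable between-arm estimate, and the cycle 1 tables do not confine the comparison to equal randomised follow-up. The size is a 16 to 47% chance of a BOTOX-only pattern per event at equal true rates of 2% down to 0.5%, and an upper limit of about 4% for a 0/90 cell.

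These figures assume safety arms close to the planned 270 and 90, and independent participants. The event rates are illustrative. The follow-up concern also assumes that BOTOX delays return to grade 4; the plan does not quantify by how much.

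A reader might go further and infer that the tables are biased or that the trial cannot assess safety. The documents do not support either: the percentages are valid, listings are planned, and the efficacy analysis, error control and sample size are unaffected.

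**What to change.** In Protocol 9.4.2.1 and SAP 10.2 to 10.4, add one table limited to Day 1 to Day 180 and to events before any open-label injection. Show n (%) per arm and the BOTOX minus placebo risk difference with Miettinen-Nurminen (score) 95% CI for:

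- any TEAE, treatment-related TEAEs, TESAEs, AESIs and PDSOT events, regardless of frequency;
- the more frequent preferred terms, with the cut-off fixed in the SAP before unblinding.

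The first group needs to be free of any threshold, both because a cut-off removes most of the uncommon terms at issue and because Protocol 9.4.2.1 makes the serious-event summary table conditional on five or more participants. Label the table as estimation only, with no tests and outside the familywise error set.

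Leave vital signs descriptive. Intervals for 5 parameters (SAP 10.5) at 6 Period 1 visits would add 30 unadjusted comparisons, of which 30 × 0.05 = 1.5 would be expected to exclude zero by chance, for little gain.

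The cost is a few lines of text and one extra table. It must be separate from the cycle 1 tables because its time window differs. No new data are needed. The downside is some unadjusted intervals that could be over-read, which the label limits. If the sponsor prefers not to add the table, the objective should be reworded as descriptive.

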9.4.2.2. Vital Signs

Descriptive statistics for vital signs (systolic and diastolic blood pressure, pulse rate, and respiratory rate) at baseline and changes from baseline at each assessment will be presented by study intervention.

9.5. Interim Analyses

Interim analyses are not planned for this study.

10. Supporting Documentation and Operational Considerations

10.1. Appendix 1: Regulatory, Ethical, and Study Oversight Considerations

10.1.1. Regulatory and Ethical Considerations

- This study will be conducted in accordance with the protocol and with the following:
 - Consensus ethical principles derived from international guidelines including the Declaration of Helsinki and CIOMS International Ethical Guidelines
 - Applicable ICH/ISO/GCP guidelines
 - Applicable laws and regulations
- The protocol, protocol amendments, ICF, investigator's brochure, and other relevant documents (eg, advertisements) must be submitted to an IRB/IEC by the investigator and reviewed and approved by the IRB/IEC before the study is initiated.
- Any amendments to the protocol will require IRB/IEC approval before implementation of changes made to the study design, except for changes necessary to eliminate an immediate hazard to study participants.
- The investigator will be responsible for the following:
 - Providing written summaries of the status of the study to the IRB/IEC annually or more frequently in accordance with the requirements, policies, and procedures established by the IRB/IEC
 - Notifying the IRB/IEC of SAEs or other significant safety findings as required by IRB/IEC procedures
 - Providing oversight of the overall conduct of the study at the site and adherence to requirements of applicable local regulations, for example 21 CFR, ICH guidelines, the IRB/IEC, and European regulation 536/2014 for clinical studies (if applicable)

10.1.2. Financial Disclosure

Investigators and subinvestigators will provide the sponsor with sufficient, accurate financial information as requested to allow the sponsor to submit complete and accurate financial certification or disclosure statements to the appropriate regulatory authorities. Investigators are responsible for providing information on financial interests during the course of the study and for 1 year after completion of the study.

10.1.3. Informed Consent Process

- The investigator or his/her representative will explain the nature of the study to the
 participant or his/her legally authorized representative and answer all questions regarding the
 study.
- Participants must be informed that their participation is voluntary. Participants will be required to sign a statement of informed consent that meets the requirements of 21 CFR 50, local regulations, ICH guidelines, HIPAA requirements, where applicable, and the IRB/IEC or study center.
- The medical record must include a statement that written informed consent was obtained before the participant was enrolled in the study and the date the written consent was obtained. The authorized person obtaining the informed consent must also sign the ICF.
- Participants must be re-consented to the most current version of the ICF(s) during their participation in the study, if applicable.
- A copy of the ICF(s) must be provided to the participant or the participant's legally authorized representative.

10.1.4. Data Protection

- Participants will be assigned a unique identifier. Any participant records or datasets that are transferred to the sponsor will contain the identifier only, participant names or any information which would make the participant identifiable will not be transferred.
- The participant must be informed that his/her personal study-related data will be used by the sponsor in accordance with local data protection law. The level of disclosure must also be explained to the participant.
- The participant must be informed that his/her medical records may be examined by Clinical
 Quality Assurance auditors or other authorized personnel appointed by the sponsor, by
 appropriate IRB/IEC members, and by inspectors from regulatory authorities.

10.1.5. Posting Clinical Study Data

- Study data and information may be published in nonpromotional, peer-reviewed publications either by or on behalf of the sponsor.
- Clinical study reports, safety updates, and annual reports will be provided to regulatory authorities as required.
- Company-sponsored study information and tabular study results will be posted on the US National Institutes of Health's website www.ClinicalTrials.gov and other publicly accessible sites.

10.1.6. Data Quality Assurance

- All participant data relating to the study will be recorded on printed or electronic CRFs
 unless transmitted to the sponsor or designee electronically. The investigator is responsible
 for verifying that data entries are accurate and correct by physically or electronically signing
 the CRF.
- The investigator must maintain accurate documentation (source data) that supports the information entered in the CRF.
- The investigator must permit study-related monitoring, audits, IRB/IEC review, and regulatory agency inspections and provide direct access to source data documents.
- The sponsor or designee is responsible for the data management of this study including quality checking of the data.
- Study monitors will perform ongoing source data verification to confirm that data entered
 into the CRF by authorized site personnel are accurate, complete, and verifiable from source
 documents; that the safety and rights of participants are being protected; and that the study is
 being conducted in accordance with the currently approved protocol and any other study
 agreements, ICH GCP, and all applicable regulatory requirements.
- Records and documents, including signed ICFs, pertaining to the conduct of this study must be retained by the investigator as stated in the clinical trial agreement. No records may be destroyed during the retention period without the written approval of the sponsor. No records may be transferred to another location or party without written notification to the sponsor.

